Examining the effects of a posterolateral mobilization with movement compared to a posterolateral self-mobilization with movement and dynamic stretching on hip internal rotation limitations: A randomized control trial

2/16/2020

University of South Carolina Protocol

Study Title: Examining the effects of a posterolateral mobilization with movement compared to a posterolateral self-mobilization with movement and dynamic stretching on hip internal rotation limitations: A randomized control trial

Principal Investigator Name: [name]

Faculty Mentor Name (if applicable): [name]

- 1) *If there is a written grant proposal, dissertation, or thesis, or your professor has provided you with a template, you are not required to use this template. However, this template should be used as a reference so that you are aware of the issues that should be addressed.*
- 2) *Texts in italics are instructions, which should be deleted. Modify as appropriate to your study.*
- 3) *Once protocol is complete, save it as a Word document. Go back to the IRB application and upload the protocol.*

A. SPECIFIC AIMS

List the broad, long-term objectives and the goal of the specific research proposed, e.g., to test a stated hypothesis, create a novel design, solve a specific problem, challenge an existing paradigm or clinical practice, address a critical barrier to progress in the field, or develop new technology.

The goal of this study is to compare the efficacy of three clinical interventions intended to treat hip dysfunctions such as hip osteoarthritis. Physical therapists utilize mobilization with movement clinically to increase range of motion that has been limited by hip pathology. This study will compare mobilization with movement administered by a physical therapist, self-administered mobilization with movement, in which patients are instructed in the maneuver and then perform it at home, and dynamic stretching as instructed by a physical therapist. Efficacy will be judged through changes in hip internal rotation range of motion, a motion which is typically limited in patients with hip pathology.

Our objectives are to quantify the effects of two different modalities of hip mobilization with movement and dynamic stretching in terms of hip internal rotation increases, and to inform current physical therapy practice by filling gaps in the literature surrounding the therapeutic effects of hip mobilization with movement. This study is intended to better equip physical therapists to select the most appropriate evidence-based interventions, thereby increasing the quality of patient care.

B. BACKGROUND AND SIGNIFICANCE

Briefly sketch the background leading to the present application, critically evaluate existing knowledge, and specifically identify the gaps that the project is intended to fill. If the aims of the study are achieved, state how scientific knowledge or clinical practice will be advanced.

Minimal evidence exists comparing the therapeutic effects of variations of mobilization with movement on the hip, but the evidence that does exist shows promising results, with participants gaining increases in functional range of motion from the interventions. There is a significant amount of research regarding mobilization with movement at joints throughout the body, but little that specifically examines internal rotation at the hip. Studies exist that evaluate and compare physical therapist-directed mobilization with movement and self-administered mobilization with movement, with only a single study comparing these two interventions specifically for hip internal rotation, and none which include a dynamic stretching

University of South Carolina Protocol

control group. Stretching is a commonly used physical therapy intervention for range of motion limitations and provides an appropriate foundation and context with which to compare mobilization with movement interventions.

This study will improve physical therapy practice by addressing the nonexistent literature comparing the effects of physical therapist-administered mobilization with movement, self-administered mobilization with movement, and dynamic stretching. Achieving this study's goals and objectives will provide physical therapists with greater evidence to select the most effective treatment interventions to administer to patients, making physical therapy more conducive to functional range of motion gains for the patient.

C. PRELIMINARY STUDIES

Surveys/Instruments, Devices, or Other Measures: Baseline bubble inclinometer to measure each participant's hip internal rotation will be used throughout the data collection. A Mulligan mobilization belt will also be used for two of the treatment groups in order to apply the mobilization at the hip required for the mobilization with movement technique.

Groups will be randomized using a random number generator with a proposed number of approximately 15-20 participants in each of the three groups. Participants will also be grouped by level of severity of the limitation in ROM, ranging from severe limitations to mild limitations. The mild limitation group will have from 25-30 degrees of IR at the hip, moderate will be 20-24 degrees, and severe will be <20 degrees. To ensure that participants are evenly spread out between the three treatment groups in regards to the severity of their limitation, they will roll a die which will determine in which of the three treatment groups they will be placed in. Only the therapist will know how the participants are grouped based on the die roll to make sure the researchers are blinded to the groups.

Data Analysis: Statistical analysis will be performed using SPSS with a Repeated Measures Analysis of Variance (ANOVA) in order to determine significance between the three groups while also using time as an outcome pre-and-post-test. Significance will be set at $p < .05$ which establishes a 95% confidence interval. A one-way ANOVA will be performed first to determine whether the groups are different at baseline, followed by a repeated measure ANOVA with a within factor and a between group factor. This will reveal the main effects of time, group, and a time by group interaction. ANOVA tests are used to determine whether there are significant measures between two or more groups and allows for comparison of multiple sample means to assess whether there is a significant difference between groups and within the same group from pre and post intervention. F values will be calculated using SPSS software to assess for any significant differences. Post-Hoc testing will be conducted if a significant F value is found in order to determine where the differences exist using three Paired t-tests, one for each group.

E. PROTECTION OF HUMAN SUBJECTS

1. TARGET POPULATION:

Participants will be recruited through in person interview from the University of South Carolina Doctor of Physical Therapy program graduate students and Wingate Doctor of Physical Therapy program. The targeted population is college-aged individuals. Inclusion criteria will be that participants must have less than 30 degrees of hip internal rotation (HIR) in at least one hip. Previous studies have suggested that HIR of less than 30 degrees has been correlated with an increase in injuries to the lower back and lower extremities.^{21,22} Exclusion criteria will include any traumatic injury within the last six months, any known skeletal deformities limiting activity such as femoro-acetabular impingement or fractures, surgeries within the last 6 months, positive findings in the Flexion, Adduction, Internal Rotation (FADDIR) or Flexion, Abduction, External Rotation (FABER) tests for hip impingement pathology depicted in figures 3 and 4 below, and any presence of OA, rheumatoid arthritis, or neurological

University of South Carolina Protocol

conditions which could negatively impact findings. Anticipated sample size is between 45-60 participants.

2. RECRUITMENT PLANS:

Participants will be recruited through in-person interview and conversation during the Fall Seminar class for DPT students. The study will be described through verbal presentation and a sign-up sheet will be passed around for interested participants where they will be asked to provide their name and email address for further communication pertaining to the study in terms of location and scheduled dates. Only interested participants that fill out the sign-up sheet will be contacted regarding participation in the study.

3. EXISTING DATA/SAMPLES:

If the investigator plans to utilize data or samples that are in existence (the investigator will not be recruiting/consenting subjects), describe where the data/samples are housed, how the investigator will gain access to the data/samples, whether the data/samples contain any direct identifiers (e.g., names, address, telephone numbers) or are coded and who will have access to the key to the code (i.e., will the USC investigator have access to key), whether the investigator will sign any data use agreement, and how data will be recorded by USC investigator.

4. CONSENT/ASSENT:

All participants will have to sign an informed consent form in order to participate in the study which outlines the expected timeline of the study, the requirements of participation, and the option to opt out of the study at any time if someone chooses to do so. The informed consent form has been uploaded onto the eIRB at this time for review.

5. POTENTIAL RISKS:

There are minimal risks that can occur during the study as we are only performing a mobilization with movement at the hip joint using external measures such as a Mulligan mobilization belt. The only side effects that can occur from performing the technique is increased range of motion at the hip or possible discomfort from increased range of motion at the hip. If any participants experiences any pain or discomfort during the interventions provided, the technique will be stopped and will be re-assessed before continuing with that specific participant to limit any source of discomfort.

6. POTENTIAL BENEFITS:

The potential benefits for participants is increased range of motion at the hip, specifically for hip internal rotation. The benefit to others includes the potential that clinicians may be able to assign a self-mobilization with movement for patients at home if it proves to be just as effective as the therapist-performed-mobilization with movement. This would allow clinicians to focus on other interventions while patients are in the clinic and hopefully have better long-term outcomes.

University of South Carolina Protocol

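### The protocol names two mechanisms as deciding the arm, a random number generator and a participant's die roll, without saying how they relate, and the die route is not secured against a repeated or re-mapped roll

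*Protocol*

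**What the plan says.** Everything at issue stands in one Protocol paragraph, the one on group assignment immediately before Data Analysis.

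- It opens with the generator: "Groups will be randomized using a random number generator with a proposed number of approximately 15-20 participants in each of the three groups".
- It then defines three severity bands: "The mild limitation group will have from 25-30 degrees of IR at the hip, moderate will be 20-24 degrees, and severe will be <20 degrees".
- It then names a second mechanism, a roll by each participant: "they will roll a die which will determine in which of the three treatment groups they will be placed in".
- The aim given for that roll is balance on severity: "To ensure that participants are evenly spread out between the three treatment groups in regards to the severity of their limitation".
- It closes on who knows the result: "Only the therapist will know how the participants are grouped based on the die roll to make sure the researchers are blinded to the groups".

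Section E.1 (Target Population) gives the total: "Anticipated sample size is between 45-60 participants".

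**The concern.** Two sentences each name something that fixes the arm. None says, for example, that the generator sets the die-to-arm key, or that one method works within severity bands and the other overall. Two teams following this text in good faith could run different allocation procedures.

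The routes do not protect the comparison equally. A generator can produce a complete list before enrolment, which can be kept and compared with what happened. A die is rolled live, one participant at a time, and here a single person translates the roll into an arm. If that person also treats, a roll could be repeated, or the meaning of a face changed, and nothing in the available text would show it. Allocation cannot be repaired once participants have been assigned, and the three-arm comparison rests on it.

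**Working it through.** **Step 1: the stated sizes.** Inputs are 15-20 per arm and three arms (group-assignment paragraph) and 45-60 in total (section E.1). 3 × 15 = 45 and 3 × 20 = 60, so the sizes agree. The available text gives no power, effect size or SD, so there is no power figure to reproduce.

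**Step 2: the two routes side by side.**

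| | Random number generator | Die roll |
|---|---|---|
| Said to decide the arm | Yes | Yes |
| Stated purpose | Form three groups of about 15-20 | Even spread of severity |
| Who produces the result | Not stated | The participant |
| Who knows the mapping to arms | Not stated | Only the therapist |
| Relation to the other route | Not stated | Not stated |

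**Step 3: are the routes interchangeable on arm size?** Assume a fair die, two faces per arm (the document gives no mapping) and independent rolls. The arm sizes a, b, c are then multinomial, and

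P(all arms 15-20) = Σ N! / (a! b! c!) / 3^N, summed over a + b + c = N with each of a, b, c between 15 and 20.

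| N | All arms 15-20 | At least one arm below 15 |
|---|---|---|
| 45 | 1.8% | 98.2% |
| 48 | 15.6% | 84.4% |
| 51 | 32.9% | 64.6% |
| 54 | 31.3% | 45.4% |
| 57 | 13.3% | 29.9% |
| 60 | 1.4% | 18.8% |

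The rows for 45 and 60 are harsh, because there the range is met only by exactly equal arms. The middle rows are the fairer test, and even they reach only about one in three. A list prepared in advance can hold the arm sizes; an unrestricted roll cannot.

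**Step 4: severity.** The document gives no stratum sizes, so these are assumptions. Under the same die model, the chance that the largest and smallest arms within one severity band differ by 4 or more is 37% for a band of 10, 50% for 15 and 61% for 20. Independent rolls are simple randomization and do not use the band, so they cannot ensure the even spread for which the die was introduced.

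**Step 5: security of the die route.** The text gives one holder of the mapping. It does not say when the mapping is fixed, whether rolls are recorded, or whether baseline is measured before the roll.

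**The case against.** **The two sentences may describe one thing.** A die is, loosely, a random number generator. The paragraph does not say so, and it gives the die its own purpose, severity balance, which reads as a separate step. If the die is the generator after all, the plan is simply the live roll, and steps 3 to 5 apply in full.

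**A reader might infer that allocation is neither concealed nor checkable.** The document does not support that. Nobody can foresee a fair roll, and foreknowledge is what concealment guards against. The text also intends to keep the grouping from the researchers. The absence of a log, witness or fixed key is silence, and part of the protocol ahead of this paragraph was not available. What stands is narrower: the available text does not secure the allocation against a repeated or re-mapped roll. Missing text elsewhere cannot remove a conflict between two sentences that both stand here.

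**A reader might infer that the treating therapist controls assignment.** The wording is "Only the therapist will know how the participants are grouped based on the die roll", and its stated purpose is blinding. Whoever delivers an arm must know it. That this person treats is likely, since section A has a physical therapist administer one arm and instruct another, but the document does not state it.

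**A reader might infer that participants will be steered, and put a figure in degrees on it.** Nothing in the document suggests that steering is expected, and any such figure needs an invented number of redirected participants and an invented difference in gain. The planned baseline one-way ANOVA might also reveal steering by stiffness. With 15-20 per arm it is a weak check, and it would miss selection on something unmeasured, such as willingness.

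**The text says approximately.** So arms outside 15-20 are not a strict breach. Agreed; step 3 shows only that the two routes are not equivalent.

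**Conclusion.** The point holds as an unreconciled inconsistency in a core design step. Two mechanisms are each said to decide the arm, and the paragraph cannot be carried out until one is chosen or their relation is stated. Its secondary part also holds: under the die route the mapping rests with one person, and the available text describes no protection against a repeated or re-mapped roll.

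The effect on the treatment comparison cannot be quantified. The only computed sizes concern balance, and they rest on a fair die with two faces per arm, independent rolls and, for severity, assumed band sizes. The point does not show that allocation is unconcealed, that it has been or will be manipulated, or that no record exists. It should be corrected before enrolment.

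**What to change.** Rewrite the paragraph around one mechanism:

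1. Delete the die. Use the random number generator already named to prepare the whole allocation list before the first participant.
2. Make it a blocked list, stratified by the three severity bands. This keeps both stated aims, an even severity spread and about 15-20 per arm, which simply removing the die would not do. Varying the block size makes the next assignment harder to guess for a therapist who knows earlier ones.
3. Have an existing team member who does not enrol, treat or measure hold the list, and name that role.
4. Release each assignment, for example by numbered sealed envelope, only after consent, baseline hip internal rotation and severity band are recorded. Keep a dated log of each release.

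The cost is one paragraph of protocol text, a small administrative task and the need to name a list-holder. The document does not show whether someone outside enrolment, treatment and measurement is already on the team, so the investigator should confirm this. Envelopes are one workable means of release; any method that keeps the next assignment hidden until baseline is recorded, and leaves a record, would serve.

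### Two allocation methods are named and neither is restricted, so 15-20 per arm is only the expected arm size for 45-60 participants

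*Protocol*

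**What the plan says.** The paragraph on group assignment, just before Data Analysis, opens with one method: "Groups will be randomized using a random number generator with a proposed number of". The size it proposes there is "approximately 15-20 participants in each of the three groups". It then defines three severity bands by degrees of hip internal rotation and gives a second method, under which "they will roll a die which will determine in which of the three treatment groups they will be placed in". The purpose stated for that second method is this: "To ensure that participants are evenly spread out between the three treatment groups in regards to the severity of their limitation".

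Section E.1, Target Population, gives the total: "Anticipated sample size is between 45-60 participants".

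The paragraph does not say how the generator and the die relate to each other. It mentions no block, prepared list, quota or separate assignment scheme for each severity band. Part of the protocol between the heading C. Preliminary Studies and the paragraph on instruments was not available, so any restriction stated there could not be checked.

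**The concern.** The per-arm range is the total divided by three. That describes what each arm will hold only if something keeps the arms level. A die roll by each participant does not, and neither does a generator used as a simple random draw, because each new assignment ignores how many people are already in each arm. Arm sizes then vary by chance, and the smallest arm falls below the average.

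Two things are at stake. First, 15-20 is the only figure in the available text for how much information each arm will carry, and a comparison of arms is limited by its smaller members. Second, the die is justified as a way to ensure an even spread of severity, which an unrestricted roll cannot ensure either. Anyone carrying out the plan must also choose between two methods without guidance.

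**Working it through.** **Inputs.** Total N = 45 to 60 (section E.1). Three arms of about 15-20 (group-assignment paragraph). Assumed: independent assignments with probability 1/3 per arm. No ratio is stated, but the same size for every arm implies equal allocation. A fair three-way die and a simple random number generator give the same distribution.

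**The plan's own figure.** 45/3 = 15 and 60/3 = 20. The 15-20 is reproduced exactly, and N/3 is also the expected arm size under the die.

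**Spread of one arm.** The standard deviation is √(N × 1/3 × 2/3) = √(2N/9), which is √10 = 3.2 at N = 45 and √13.3 = 3.7 at N = 60.

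**All three arms together.** The probability of sizes (a, b, c) with a + b + c = N is N!/(a! b! c! 3^N). Summing over all combinations gives:

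| | N = 45 | N = 52 | N = 60 |
|---|---|---|---|
| All arms in 15-20 | 1.8% | 34.8% | 1.4% |
| All arms in 13-22 | 39% | 70% | 31% |
| All arms in 12-23 | 61% | 82% | 50% |
| Mean gap, largest minus smallest | 6.5 | 7.0 | 7.6 |
| Gap of 5 or more | 71% | 72% | 77% |

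N = 52 is the most favourable total for each of the three bands. The chance of a gap of 5 or more dips to 69% at N = 46, its lowest value in the range.

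**Ordered arms.** At N = 45 the smallest, middle and largest arms average 11.8, 14.9 and 18.3. At N = 60 the smallest averages 16.3 and the largest 23.8. The smallest arm is below 15 with probability 98% at N = 45, 45% at N = 54, 40% at N = 55 and 19% at N = 60.

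**Cost in precision.** For two arms of sizes a and b, the variance of the difference relative to equal arms is (1/a + 1/b) ÷ (6/N). Averaged over the distribution, this is 1.05 at N = 45 and 1.037 at N = 60. A typical smallest pair at N = 45, 12 v 15, gives (1/12 + 1/15) ÷ (2/15) = 0.150 ÷ 0.133 = 1.125.

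For scale, take a two-sample t-test with 80% power and two-sided 0.05. The detectable difference is 1.06 SD at 15 v 15, 1.08 SD at 12 v 18 and 1.13 SD at 12 v 15. This test is only a yardstick. The protocol plans a repeated-measures ANOVA.

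**A tempting remedy that fails.** Take one list of 60 slots, 20 per arm, drawn without replacement. If enrolment stops at 45, the chance of 15 in every arm is C(20,15)³ ÷ C(60,45) = 15,504³ ÷ (5.32 × 10¹³) = 7.0%. Fixed totals hold only if the list is used up.

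**Permuted blocks.** With blocks of 3 and 6, stopping part-way through a block leaves two arms at most 2 apart. With a separate list in each of three severity bands, the gap can reach 3 × 2 = 6 only if all three lists stop at their worst point in the same direction. Under unrestricted allocation, the average gap is already 6.5 to 7.6.

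**The case against.** The strongest reply is that nothing is miscalculated. The figure is a proposal, worded as approximate, and equals the expected arm size. That stands: the per-arm range and the total are consistent. A reader might infer from the 1.8% and 1.4% that the plan almost never yields what it states. The text does not support that reading, because at N = 45 and N = 60 the strict band admits only 15/15/15 or 20/20/20. Allowing two either side raises the chance to 31-70% over the recruitment range.

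The second reply is that the sentence with 15-20 names the generator, not the die, and a restricted computer list would deliver those sizes. This also stands in part. However, no restriction is described, and a simple generator behaves exactly like the die. The generator sentence therefore does not rescue the figure. It adds a conflict that has to be settled.

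Third, a reader might infer that the smaller arms will usually fall short of 15 throughout. That holds at the low end of recruitment but not from about N = 54 upward. At N = 60 the smallest arm is below 15 in only 19% of draws, and the strict band fails mostly because some arm exceeds 20.

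Fourth, the loss is small and no stated power claim is undermined. That is correct and limits the weight of the point.

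Leaving the matter to the statistical analysis plan is not an answer, because the protocol itself sets both the allocation procedure and the arm size.

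**Conclusion.** The point holds as one about an unspecified and unrestricted allocation method, not as an arithmetic error. As described, the plan gives arms of 15-20 on average. The smallest arm averages about 12 if 45 enrol and about 16 if 60 enrol, and arms 5 or more apart are the usual outcome. The average loss is about 4-5% in the variance of a comparison of two arms, so this does not threaten the trial's validity. It is worth correcting because the remedy is nearly free and also resolves the conflict between generator and die.

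The conclusion rests on independent assignments with equal probabilities, and on there being no restriction in the part of the protocol that was not available. A block or list described there would remove the point about arm sizes; the two methods would still need reconciling.

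**What to change.** Replace both methods with one computer-generated, concealed list in small permuted blocks of randomly mixed size, for example 3 and 6. Preferably prepare a separate list for each of the three severity bands already defined. Arm sizes then stay close to equal wherever enrolment stops between 45 and 60, and the even spread of severity that the die was meant to give is built in. Do not use a single 60-slot list with equal totals, for the reason shown in the working.

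If the die is kept, delete the reference to the generator or explain its role, and restate the figure along these lines: expected 15-20 per arm; smallest arm about 12 if 45 enrol and about 16 if 60 enrol.

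The cost is preparing the list and rewriting a sentence or two of the protocol, with no extra participants. The one drawback is slight predictability near the end of a block, which mixed block sizes and concealment limit.

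### An unrestricted die roll cannot guarantee an even spread of severity across the three groups, and the protocol also names a random number generator for the same allocation step

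*Protocol*

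**What the plan says.** In the protocol, the paragraph just before Data Analysis opens: "Groups will be randomized using a random number generator with a proposed number of approximately 15-20 participants in each of the three groups". It then sorts participants into three severity levels by baseline hip internal rotation: "The mild limitation group will have from 25-30 degrees of IR at the hip, moderate will be 20-24 degrees", with severe below 20 degrees. Next comes the die, introduced together with its purpose: "ensure that participants are evenly spread out between the three treatment groups in regards to the severity of their limitation, they will roll a die". The result of the roll fixes the treatment group. The sentence after that again treats the die roll as the source of the grouping, known only to the therapist.

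The text available describes no block, no separate list per severity level, no quota and no minimization. Data Analysis specifies a one-way ANOVA at baseline and then a "repeated measure ANOVA with a within factor and a between group factor"; severity does not appear in that model. Section E.1 gives the size: "Anticipated sample size is between 45-60 participants".

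**The concern.** Two things are wrong in one paragraph.

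**The claim does not fit the method.** Each roll ignores the participant's severity and everyone assigned before. Sorting people by severity first and then rolling is still simple randomization within each level. It balances on average over many trials; it does not guarantee balance in this one. Nor does it hold the groups to about 15–20 each.

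**One step has two mechanisms.** The generator and the die are both said to allocate participants to the three groups. Staff cannot tell from this paragraph which one assigns a given participant.

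The sponsor chose severity as the factor to balance, and the die is the only stated means of doing so. The one-way ANOVA at baseline looks at the same measurement but corrects nothing. If gains in rotation differ by severity (an assumption; the protocol does not say so), a chance imbalance would enter the time-by-group comparison unadjusted.

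A smaller point concerns the bands. The mild band runs up to 30 degrees, while section E.1 says that "participants must have less than 30 degrees of hip internal rotation (HIR) in at least one hip". Readings between 24 and 25 degrees belong to no band unless readings are whole degrees.

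**Working it through.** **Inputs.** Three groups of about 15–20 (randomization paragraph); total 45–60 (section E.1); equal allocation, implied by the group sizes; no restriction on the rolls. Stratum sizes are not given and are assumed below.

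**The plan's own figure.** 3 × 15 = 45 and 3 × 20 = 60, so the stated total follows from the group sizes. No power calculation is given in the text available.

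**Formula.** For independent rolls with probability 1/3 per group, the chance of group sizes (a, b, c) with a + b + c = n is n! / (a! b! c!) × (1/3)^n. Summing this over the relevant splits gives exact probabilities.

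**Overall group sizes**

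| | N = 45 | N = 52 | N = 60 |
|---|---|---|---|
| All three groups within 15–20 | 1.8% | 35% | 1.4% |
| All three groups within a looser 13–22 | 39% | 70% | 31% |

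The gap between the largest and smallest group is 5 or more in 71% of trials at N = 45 and 77% at N = 60. Over all N from 45 to 60 it runs from 69% (N = 46) to 77% (N = 60).

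**Precision.** The variance of a pairwise contrast is proportional to 1/n_i + 1/n_j. Relative to equal groups it rises on average by 5% (N = 45) and 4% (N = 60); for the worst pair, by 16% and 13%.

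**Within one severity level (size assumed)**

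| Participants in the level | Gap of 4 or more between arms |
|---|---|
| 6 | 18% |
| 9 | 32% |
| 12 | 42% |
| 15 | 50% |
| 20 | 61% |

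Two of these cases by hand:

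- An exact 5/5/5 split of 15 has probability 15!/(5!)³ / 3¹⁵ = 756,756 / 14,348,907 = 5.3%.
- With 6 severe participants, some arm receives none with probability (3 × 2⁶ − 3) / 3⁶ = 189/729 = 26%.

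With three equal levels, at least one has a gap of 4 or more with probability 1 − (1 − 0.501)³ = 88% at N = 45, and 1 − (1 − 0.614)³ = 94% at N = 60.

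**Share of severe participants** (simulated, 40,000 runs). Two arms differ by 20 percentage points or more in 40–51% of trials if a third of participants are severe, 28–39% if 20% are, and 10–16% if about 10% are. In each range the higher figure is for N = 45 and the lower for N = 60.

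**Permuted blocks for comparison** (sizes 3 and 6 mixed, within strata; simulated, 20,000 runs, three sets of stratum shares). Groups fall within 13–22 in 99.8–100% of trials, and a gap of 5 or more between groups occurs in 0.2–0.4%. The gap within a stratum never exceeds 2. That is a property of the design: complete blocks are balanced, and an unfinished block of 6 holds at most two of any arm.

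**The case against.** The strongest reply is that the consequence is small. A fair die is valid randomization. Take the time-by-group test as an ANOVA on change, with equal strata, a shift in gain of 0.4 SD per severity level and a 1 SD difference between the extreme arms. Type I error with the die is then 4.7% (N = 45) and 4.6% (N = 60). Power is:

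| | Die | Severity-balanced |
|---|---|---|
| N = 45, no adjustment | 58% | 59% |
| N = 60, no adjustment | 75% | 74% |
| N = 45, adjusted for stratum | 62% | 65% |
| N = 60, adjusted for stratum | 76% | 78% |

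This stands. Balanced allocation alone gains almost nothing; allocation and adjustment together gain 7 points (58% to 65%) at N = 45 and 3 points (75% to 78%) at N = 60.

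Other points also stand in part:

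- Severity is a banding of the pre-test value, and the time-by-group term compares changes. Differences in level are therefore already removed; only severity-dependent gain, including regression to the mean, is left.
- The 13–22 window is the reviewer's. Its low values at N = 45 and N = 60 arise because the mean then lies near one edge. With a tolerance of 5 around N/3, the figures are 81%, 70% and 71% at N = 45, 52 and 60.
- The thresholds of 4 participants and 20 points are illustrative and not tied to an inferential limit.
- The text just before the instruments paragraph was not available for this review and might explain how the generator and the die relate.

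None of this makes an unrestricted roll able to guarantee balance, and nothing in the paragraph itself reconciles the two mechanisms.

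**Conclusion.** The concern holds and should be fixed before enrolment. The randomization paragraph attributes to the die a property that it lacks, and it names two mechanisms for one step. In a trial of this size, a marked imbalance in at least one severity level is more likely than not across most plausible stratum sizes.

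The overall group-size figures are exact and rest only on independent, fair rolls. Independence is the plain meaning of a die roll, though the protocol does not state it. The severity figures rest on assumed stratum sizes. The flaw does not bias the comparison over repeated trials. Its cost is some loss of precision, exposure to a chance imbalance if gains depend on severity, and an allocation procedure that cannot be followed or reported unambiguously. The band edges are minor.

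**What to change.** Preferred change:

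1. Delete the die roll. Before enrolment, use the random number generator to prepare a list in permuted blocks, with sizes 3 and 6 mixed, separately for each of the three severity strata.
2. Conceal the list from the researchers who enrol and measure, and let the therapist open one assignment at a time.
3. Define the strata without overlap or gap and inside the eligibility rule: below 20, 20 to below 25, and 25 to below 30 degrees.
4. Enter stratum in the stated ANOVA as a main effect with its time interaction, so that the analysis matches the allocation. Do not use the full factorial: adding group-by-stratum terms would use 4 more degrees of freedom and spread 45–60 people over nine cells. Baseline rotation as a covariate is a reasonable alternative adjustment.

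This costs a few minutes to generate the list and a paragraph of wording, with no added staff or participants. Assignments become slightly more predictable, which mixing the block sizes reduces, and the additive stratum term uses 2 degrees of freedom.

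If the die is kept, describe the method as simple randomization, withdraw the claim that it secures severity balance, and remove or explain the generator. That costs only wording.
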